#### Comparator agent:

New initiation of oral risedronate (35 mg weekly). New initiation is defined as no use of risedronate in the prior 180 days before treatment initiation (washout period). New users of risedronate are not allowed to receive teriparatide within the 730 days prior to treatment initiation.

### 6.2 Preliminary Covariates:

- Age
- Combined Comorbidity Index (CCI), measured over the baseline covariate assessment period, defined as 180 days prior to and

including index date.

Covariates listed above represent only a small subset of covariates that will ultimately be controlled for in the design and analysis. We use the covariates above only for initial feasibility analyses to judge whether there is likely to be sufficient overlap between treatment groups to proceed with the study. Remaining covariates are defined only after the study has passed the initial feasibility analysis and the initial power assessment and are listed in Table 1 (**Appendix B**). Gender is not included since the study is already restricted to female subjects.

### 6.3 Outcome variables and study follow-up:

#### 6.3.1 Outcome variables

Effectiveness outcome variables of interest (definitions provided in **Appendix A**):

- **Primary outcome:** Vertebral fracture (algorithm adapted from Wright et al. 2019)
- **Secondary outcome:** Non-vertebral fracture

#### 6.3.2 Study follow-up

As-treat (AT) analysis will be conducted with treatment defined as the index drug on the day of cohort entry. Similar to the trial, the patients will be followed for 24 months. A grace period and a risk exposure window of 60 days will be considered in the primary analysis.

The follow-up will start the day after drug initiation (i.e., cohort entry date), as described in the VERO trial, and will continue until the earliest date of the following events:

- The first occurrence of the outcome of interest,
- The date of end of continuous registration in the database,
- Discontinuation of the index drugs,
- Addition of the index drug from the other group or crossover,
- End of the study period,
- Measured death event occurs,
- Nursing home admission

- Nursing home admissions are considered a censoring event because the data sources utilized typically provide little to no data on a patient, particularly on drug utilization, after admission. We will utilize this as an exclusion reason for cohorts for the same reason.

A subgroup analysis will be performed by age categorized by tertiles () emulating one of the prespecified subgroup analyses of the VERO trial (Geusens P et al. 2018).

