## 9. Balance Assessment

For teriparatide vs. risedronate

Optum CDM: <https://bwh-dope.action.com/projects/details/1640/rwrs/67726>

IBM® MarketScan®: <https://bwh-dope.action.com/projects/details/1641/rwrs/67727>

Date conducted: 03/29/21

After review of initial feasibility and power analyses, complete creation of the remaining covariates from Section 6.2. Again, using the dummy outcome of a 90-day gap in database enrollment, complete a 1:1 PS-matched analysis. The PS should include the complete list of covariates.

- Provide plot of PS distributions stratified by treatment group.

Note- Please refer to **Appendix B**.

- Report covariate balance after matching.

Note- For Table 1, please refer to **Appendix B**.

- Report reasons for censoring by treatment group.

|                                 | Overall | Referent | Exposure |
|---------------------------------|----------------|-----------------|-----------------|
| Dummy outcome                   | 0 (0%)         | 0 (0%)          | 0 (0%)          |
| Death                           | 28 (0.65%)     | 9 (0.21%)       | 19 (0.44%)      |
| End of patient enrollment       | 715 (16.5%)    | 300 (6.92%)     | 415 (9.58%)     |
| End of index exposure           | 157 (3.62%)    | 70 (1.62%)      | 87 (2.01%)      |
| Maximum follow-up time          | 442 (10.20%)   | 185 (4.27%)     | 257 (5.93%)     |
| End of index exposure           | 2775 (64.03%)  | 1522 (35.12%)   | 1253 (28.91%)   |
| Start of an additional exposure | 37 (0.85%)     | 9 (0.21%)       | 28 (0.65%)      |
| Nursing Home                    | 180 (4.15%)    | 72 (1.66%)      | 108 (2.49%)     |

- Report follow-up time by treatment group.

| Median Follow-Up Time (Days) [IQR] |                  |                         |
|---|------------------|-------------------------|
| Patient Group                      | Optum CDM | IBM® MarketScan® |
| Overall Patient Population                | 163.5 [88 - 415] | 190 [100 - 431.5]       |
| Referent - Risedronate                    | 148 [88 - 371]   | 148 [88 - 331]          |
| Exposure - Teriparatide                   | 192 [88 - 446]   | 234 [113 - 533]         |

- Report overall risk of the primary outcome.

|                         | Optum CDM | IBM® MarketScan® | Pooled |
|-------------------------|------------------|-------------------------|---------------|

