| 20   | History of excessive consumption of alcohol or abuse of drugs in the 1 year prior to Visit 2, in the opinion of the investigator.   | 
Measured 365 days prior to and including day of drug initiation in inpatient or outpatient care setting (any diagnosis position):
 
Alcohol Abuse or Dependence
ICD-9 diagnosis: 291.xx, 303.xx, 305.0x, 571.0x, 571.1x, 571.2x, 571.3x, 357.5x, 425.5x, E860.0x (CMS has not released mapping for new ICD10 for this code), V11.3x
ICD-10 diagnosis: F10.0x, K70.0x, G62.1, I42.6, 099.31x
 
OR
 
Drug Abuse or Dependence
ICD-9 diagnosis: 292.xx, 304.xx, 305.2x-305.9x, 648.3x
ICD-10 diagnosis: F11.x, F12.x, F13.x, F14.x, F15.x, F16.x, F17.2x, F18.x, F19.x, F55.2, G62.0, 099.32x
 
OR
 
Non-compliance
ICD-9 diagnosis: V45.12, V15.81
ICD-10 diagnosis: Z91.19, Z91.15
 | 
Paterno, Elisabetta et al. "Cardiovascular outcomes associated with canagliflozin versus other non-gliflozin antidiabetic drugs: population based cohort study." BMJ 2018;360:k119
http://dx.doi.org/10.1136/bmj.k119
 
Paterno, Elisabetta et al. "Empagliflozin and the Risk of Heart Failure Hospitalization in Routine Clinical Care: A First Analysis from the Empagliflozin Comparative Effectiveness and Safety (EMPRISE) Study." Circulation 2019 Apr 8. doi: 10.1161/CIRCULATIONAHA.118.039177
 |
| 21.1 | Previous treatment with the following bone active drugs is allowed but treatment must be discontinued at Visit 1 or at the time indicated below:
1. Oral bisphosphonates (including alendronate, risedronate, ibandronate, etidronate).  | 
Measured 180 days prior to and 1 day before the day of drug initiation:
 
Generic names:
Alendronate, Ibandronate, Risedronate, Etidronate, Tiludronate
   |  |
| 21.2 | 2. SERMs, calcitonin, estrogen (oral, transdermal, or injectable), progestin, estrogen analog, estrogen agonist, estrogen antagonist or tibolone, androgens, strontium ranelate, or active vitamin D3 analogues.  | 
Measured 30 days prior to and 1 day before the day of drug initiation:
 
Generic names:
SERMs: OSPEMIFENE, RALOXIFENE HCL, ESTROGENS, CONJUGATED/BAZEDOXIFENE ACETATE
Calcitonin
HRT: estrogens, progestins, androgens
  | 
Strontium not approved in USA for treatment of osteoporosis.
 
Vitamin D3 analogues over the counter
   |

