| 21.3 | Intravenous zoledronate, if the last dose was administered at least 12 months before Visit 1.   | 
Measured 365 days prior to and 1 day before the day of drug initiation:
 
Generic name:
Zoledronic Acid
   |  |
| 21.4 | Intravenous ibandronate or pamidronate, if the last dose was administered at least 3 months before Visit 1.   | 
Measured 90 days prior to and 1 day before the day of drug initiation:
 
Generic name:
Ibandronate or pamidronate
CPT codes:
C9229, J1740, C9411, J2430
  |  |
| 21.5 | Subcutaneous denosumab, if the last dose was administered at least 6 months before Visit 1.   | 
Measured 180 days prior to and 1 day before the day of drug initiation:
 
Generic name:
Denosumab
   |  |
| 21.6 | Fluoride unless given at therapeutic doses (> 20 mg/day) for more than 3 months in the 2 years prior to Visit 1, or for more than a total of 2 years, or at any dosages within the 6 months prior to Visit 2 (previous or current use of fluoridated water or topical dental fluoride treatment is permitted).    | N/A  | 
Sodium Fluoride is not used to treat the osteoporosis since 2001/2002 when a RCT and sub meta-analysis showed an increased of risk of fractures in the exp arm
  |
| 21.7 | Prior treatment with PTH, teriparatide, or other PTH analogs; or prior participation in any other clinical trial studying PTH, teriparatide, or other PTH analogs.  | 
Measured 730 days (2 years) prior to and 1 day before the day of drug initiation:
 
Generic names:
parathyroid hormone , teriparatide, abaloparatide
Brand names:
Abaloparatide (Reclast®), Teriparatide (Forteo®), Doseyab (Abaloparatide)
  |  |
| 22   | Known hypersensitivity to teriparatide or risedronate, or to any diluents or excipients of teriparatide or risedronate 35 mg/week oral tablet.  | N/A  |  |

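### Follow-up is not censored when a woman starts an osteoporosis drug other than the two index drugs, so part of the as-treated time is not index-drug-only time

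*Combined protocol and SAP*

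**What the plan says.** Section 6.3.2 defines the analysis: "As-treat (AT) analysis will be conducted with treatment defined as the index drug on the day of cohort entry". On duration it says: "Similar to the trial, the patients will be followed for 24 months". Of the events that end follow-up, two concern treatment:

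- "Discontinuation of the index drugs"
- "Addition of the index drug from the other group or crossover"

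On the tail after the last supply it says: "A grace period and a risk exposure window of 60 days will be considered in the primary analysis". It does not say whether the two windows run together or add up.

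At entry the plan is much stricter about other bone-active drugs. Appendix A, criterion 21.1, screens 180 days before index for "Alendronate, Ibandronate, Risedronate, Etidronate, Tiludronate". Neighbouring criteria cover SERMs, calcitonin and hormone therapy (30 days), zoledronic acid (365 days), intravenous ibandronate or pamidronate (90 days), denosumab (180 days), PTH analogues (730 days) and romosozumab (180 days). All these look-backs end the day before initiation. No counterpart applies after index, and section 13.2, reserved for sensitivity analyses, is blank.

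**The concern.** The plan treats these drugs as disqualifying up to the day before index and does not mention them afterwards. An as-treated analysis is meant to compare time on teriparatide with time on risedronate. Under the written rule, two kinds of other time enter the comparison:

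- **Add-on.** A woman who keeps refilling the index drug and also receives, say, denosumab meets no censoring event for it, and can contribute such time up to the 24-month limit.
- **Switch.** A woman who stops the index drug and starts another one is censored for discontinuation, but only once the window has run out. Fractures in the window count against the index drug.

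The drugs started, and how often, may differ between arms, so the two contributions need not cancel. The study exists to see whether 0.44 is reproduced. A shift caused by third-drug time could be misread as a failed, or a successful, replication.

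**Working it through.** **1. The plan's own power figure.** Section 10, pooled: 4,334 × 17.80/1,000 = 77.1452 events, HR 0.44, two-sided alpha 0.05, 1:1 matching. Power = Φ(|ln 0.44| × √(77.1452/4) − 1.960) = Φ(0.8210 × 4.3916 − 1.960) = Φ(1.645) = 0.950. This agrees with the stated 0.950063, so the power table is not in dispute.

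**2. How follow-up ends.** In the section 9 censoring table the rows sum to 4,334. End of index exposure accounts for 2,775 (64.0%): 1,522/2,167 = 70.2% of risedronate and 1,253/2,167 = 57.8% of teriparatide women. A second row with the same label adds 157 (3.6%). Start of an additional exposure accounts for 37 (0.85%): 9 risedronate and 28 teriparatide. The table does not define that row.

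**3. Length of the window relative to follow-up** (section 9 medians).

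| Arm | Median, days | 60 days as share | 120 days, if the windows add |
|---|---|---|---|
| Risedronate, both databases | 148 | 41% | 81% |
| Teriparatide, Optum | 192 | 31% | 63% |
| Teriparatide, MarketScan | 234 | 26% | 51% |

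These are not contaminated shares. The window also covers women who stop and start nothing.

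**4. What share could the switch route contaminate?** Share c = d × p × w / m, where d is the proportion discontinuing, p the proportion of those who switch at once, w the window and m mean follow-up. The documents give d = 0.64 and w = 60 (possibly 120). Assumptions: p = 10–50% and m = 200–300 days.

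- w = 60: from 0.64 × 0.10 × 60/300 = 1.3% to 0.64 × 0.50 × 60/200 = 9.6%.
- w = 120: from 2.6% to 19.2%.

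For teriparatide alone, d = 0.578. Averaging the three quartiles gives a rough mean of (88 + 192 + 446)/3 = 242 days in Optum and (113 + 234 + 533)/3 = 293 in MarketScan, so take m = 250–300. With w = 60:

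- c = 2% needs p = 14–17%.
- c = 5% needs p = 36–43%.
- c = 10% needs p = 72–87%.
- c = 15% needs p = 108–130%, which is impossible.

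Add-on time would come on top, and the documents contain nothing from which to estimate it.

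**5. Effect on the hazard ratio.** Assume a share c of teriparatide time carries a risedronate-like hazard. The observed HR is then 0.44(1 − c) + c. Power uses the formula in step 1 with events held at 77.1.

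| c | Observed HR | Power |
|---|---|---|
| 0 | 0.440 | 95.0% |
| 2% | 0.451 | 93.8% |
| 5% | 0.468 | 91.5% |
| 10% | 0.496 | 86.9% |

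If instead a share c of risedronate time carried a teriparatide-like hazard, the HR would be 0.44/(1 − c + 0.44c): 0.445 at 2% and 0.466 at 10%. If a drug added in the teriparatide arm lowered the hazard below that of teriparatide alone, the HR would read below 0.44. The direction therefore depends on which drug is started and in which arm.

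**6. Are these drugs common in this population?** In section 5.3 the oral bisphosphonate exclusion removed 499 + 1,024 = 1,523 of 5,385 + 9,523 = 14,908 otherwise eligible initiators (10.2%). This counts people before index, not time after it. It makes later use plausible but does not measure it.

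**The case against.** The strongest reply is that discontinuation already censors most women, so the rule largely polices itself. That is right as far as it goes. A reader might infer that switchers go on counting in their index arm without limit. The documents do not support this, because stopping the index drug is a listed event and the commonest reason for censoring. Only add-on users escape altogether, and their number is unknown.

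A reader might also infer that the 37 women show the rule missing most switches. That does not follow either. The row is undefined, and a low count may simply mean little crossover. If the row already includes other drugs, section 6.3.2 should say so.

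The shift is modest. An HR of 0.45–0.50 lies well inside the trial's interval of 0.29 to 0.68 (section 1.6). The dilution formula also gives the third drug its full effect at once and the index drug no carry-over, which tends to enlarge the figure.

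Censoring at the new drug has a cost of its own: if the drug is started because the disease is worsening, the censoring is informative. This stands, and is a reason to show both analyses. The plan already accepts the same risk by censoring at discontinuation and crossover.

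Finally, the design diagram and the linked code folder could not be seen. They may bear on what was implemented, but they do not alter the written rule.

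**Conclusion.** The omission is real and certain on the text: no listed event covers the start of an osteoporosis drug other than the two index drugs, and no sensitivity analysis covers it. Its consequence is uncertain. With the 60-day window and 10–50% of discontinuers switching at once, the switch route would affect about 1–10% of follow-up. If the two windows add to 120 days, it would affect about 3–19%. At 2–10% of teriparatide time with a risedronate-like hazard, 0.44 would read 0.45–0.50. These figures rest on assumed switching rates, an assumed mean follow-up and an assumed effect of the third drug. They are illustrations, not estimates, and they leave out add-on use. It would go too far to say that the contrast is known to be seriously diluted, or that the bias must be towards 1. This is a cheap improvement to the plan, not a flaw that invalidates it.

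**What to change.** In section 6.3.2, add a censoring event: the first dispensing or administration after index of any osteoporosis drug other than the index drug. Use the Appendix A lists already built: other oral bisphosphonates, zoledronic acid, intravenous ibandronate or pamidronate, denosumab, PTH analogues, romosozumab, and raloxifene and calcitonin. Remove each arm's own drug from the list applied to it, since risedronate appears in criterion 21.1 and teriparatide in 21.7.

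Leave hormone therapy out. It is screened for only 30 days before index, and Appendix B shows 131/2,167 (6.0%) and 137/2,167 (6.3%) users in the matched arms.

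Also:

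- Report the new censoring reason by arm in Table 3 (section 14.3), and define the row for start of an additional exposure.
- State whether the grace period and the risk window run together or add up, and explain the two rows labelled end of index exposure.
- In section 13.2, prespecify the analysis under the current rule as a sensitivity analysis.

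The cost is a few sentences and one extra run with existing code lists, with slightly less follow-up and fewer events. The added censoring may be informative, so the two results should be read side by side.

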### 5.2 Important steps for cohort formation

New use of teriparatide (exposure) is defined as no use of the exposure drug within the 730 days (2 years) prior to index date. This will emulate the trial requirement for which treatment with teriparatide was not allowed any time before randomization. New use of risedronate (comparator) is defined as no use of the comparator drug within the 180 days prior to index date. The shorter washout period for risedronate users, compared to teriparatide users, will emulate the trial requirement of discontinuation of risedronate at the beginning of the screening period. Differently from teriparatide, history of risedronate use was allowed in the trial. New users of teriparatide are not allowed to receive risedronate within the 180 days prior to index date, and new users of risedronate are not allowed to receive teriparatide within the 730 days (2 years) prior to index date.

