#### 5.2.2 Specify inclusion/exclusion criteria for cohort entry and define the index date

Inclusion and exclusion criteria were adapted from the trial as closely as possible. Definitions for all inclusion/exclusion are provided in **Appendix A** and are summarized in the flowcharts below.

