| Excluded based on Exclusion criteria #15 - Oral bisphosphonate use                                  | -499 | 4886        | -1024 | 8499        |
| Excluded based on Exclusion criteria #16 - SERMs, Calcitonin, HRT                                   | -101 | 4785        | -321  | 8178        |
| Excluded based on Exclusion criteria #17 - Zoledronic acid use                                      | -2   | 4783        | -7    | 8171        |
| Excluded based on Exclusion criteria #18 - Intravenous ibandronate or pamidronate                   | -1   | 4782        | -1    | 8170        |
| Excluded based on Exclusion criteria #19 - Denosumab use  | -10  | 4772        | -4    | 8166        |
| Excluded based on Exclusion criteria #20 - PTH or PTH analogue use                                  | -44  | 4728        | -137  | 8029        |
| Excluded based on Exclusion criteria #21 - Romosozumab  | 0    | 4728        | 0     | 8029        |
| Final cohort  |      | 4728 |       | 8029 |

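### Section 6.3.2 promises a nursing home exclusion that the Section 5.3 flowchart does not show, so it appears not to have been applied

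*Combined protocol and SAP*

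**What the plan says.** Section 6.3.2 lists nursing home admission among the events that end follow-up. The reason given is that "the data sources utilized typically provide little to no data on a patient, particularly on drug utilization, after admission". The next sentence extends the rule from follow-up to cohort entry: "We will utilize this as an exclusion reason for cohorts for the same reason".

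Section 5.2.2 says where every entry criterion should be found: "Definitions for all inclusion/exclusion are provided in Appendix A and are summarized in the flowcharts below".

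The flowchart in Section 5.3 runs through cohort entry, enrollment, prior use, inclusion criteria #1 to #4 and exclusion criteria #1 to #21. The last row before the final cohort is "Excluded based on Exclusion criteria #21 - Romosozumab". No row concerns nursing home admission. Elsewhere in the supplied text, nursing home appears only as a censoring reason in the Section 9 table.

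New use is defined by the absence of claims. For the exposure: "New use of teriparatide (exposure) is defined as no use of the exposure drug within the 730 days (2 years) prior to index date". For the comparator: "New use of risedronate (comparator) is defined as no use of the comparator drug within the 180 days prior to index date".

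**The concern.** The plan states a cohort rule, gives a reason for it, and then reports a cohort that does not show the rule. Someone rebuilding the study from Section 6.3.2 would get a different cohort from someone following Section 5.3.

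The reason for the rule applies more strongly before the index date than after it. If drug claims are sparse during a nursing home stay, a stay inside the look-back makes a missing claim look like non-use. Three parts of the design depend on those claims:

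- the 730-day and 180-day washouts that define a new user;
- the bone-drug exclusions (Appendix A, trial criteria 21.1 to 21.7, and romosozumab);
- the medication covariates in Table 1.

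Censoring after the index date repairs none of these, because it acts only forward in time. Matching does not address the gap directly either, because Table 1 has no nursing home covariate.

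**Working it through.** **1. Does the flowchart close without the exclusion?** Inputs: the Section 5.3 rows, comprising 5 entry rows, 5 inclusion rows and 25 exclusion rows (35 in all).

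| Step | Optum | MarketScan |
|---|---|---|
| All patients | 78,202,636 | 200,203,908 |
| Failed cohort entry | −77,830,806 | −199,450,502 |
| Insufficient enrollment | −90,897 | −176,733 |
| Prior use of referent | −199,055 | −403,827 |
| Prior use of exposure | −19,897 | −44,254 |
| More than one exposure category | 0 | 0 |
| Left before the clinical criteria | 61,981 | 128,592 |
| Inclusion #1 to #4, summed | −55,544 | −117,340 |
| Left | 6,437 | 11,252 |
| Exclusion #1 to #21, summed | −1,709 | −3,223 |
| Final cohort | 4,728 | 8,029 |

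Both results equal the stated final cohorts. There is no residual in which an unlisted step could sit.

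**2. Was it applied after the flowchart but before matching?** Input: the unmatched age counts in Appendix B.

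- Optum: risedronate 46 + 906 + 1,787 + 1,136 = 3,875; teriparatide 12 + 250 + 378 + 213 = 853; total 4,728.
- MarketScan: risedronate 138 + 2,387 + 2,013 + 1,926 = 6,464; teriparatide 24 + 526 + 616 + 399 = 1,565; total 8,029.

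The totals are unchanged, so nothing was removed between the flowchart and matching.

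**3. Could the row have been left out because few women were affected?** This is unlikely. Romosozumab removes 0 and 0 patients and osteonecrosis of the jaw removes 0 and 2, and each has its own row.

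**4. What would applying it do to power?** Inputs from Section 10, pooled: 4,334 matched women, risk 17.80 per 1,000, HR 0.44, two-sided alpha 0.05, equal groups.

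Expected events d = 4,334 × 0.0178 = 77.1452. Power = Φ(√(d/4) × |ln 0.44| − 1.96) = Φ(4.392 × 0.821 − 1.96) = Φ(1.645) = 0.950, which reproduces the stated 0.950.

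The documents give no count of women admitted before or on the index date, so the cohort after the exclusion cannot be computed. The losses below are assumed, at unchanged event risk:

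| Assumed share removed | Matched N | Expected events | Power |
|---|---|---|---|
| 0% (as stated) | 4,334 | 77.1 | 95.0% |
| 1% | 4,291 | 76.4 | 94.8% |
| 5% | 4,117 | 73.3 | 94.0% |
| 10% | 3,901 | 69.4 | 92.8% |
| 20% | 3,467 | 61.7 | 89.7% |

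**The case against.** **The exclusion may sit inside another row.** Rows that sum exactly show that no row is missing, not what each row contains. The cohort entry row removes 77.8 million and 199.5 million patients and its content is not described. This stands as a possibility, and it is why the conclusion is that the exclusion appears not to have been applied. But nothing in the documents places it there, and the clinical exclusions otherwise have their own rows.

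**Part of the source is not visible.** The supplied Appendix A goes from trial exclusion 4 to 15, and the design diagram is not shown. So absence from Appendix A cannot be claimed. The finding rests on the flowchart, which does show conditions with no entry in the visible part of Appendix A, such as malignancy, end-stage renal disease and kyphoplasty.

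**The problem partly limits itself.** Cohort entry needs an observed claim for an index drug, which a current resident with sparse drug data would seldom produce. That is fair. The remaining concern is mainly women with a stay earlier in the look-back. Measured frailty is also balanced after matching (top category 41.9% against 41.7%), but a frailty score does not restore missing drug claims.

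**Two stronger readings are tempting.** In Section 9, 180 of 4,334 matched women (4.15%) are censored for nursing home. A reader might take this as a guide to how many were already admitted at entry. It is not: these events end follow-up, which starts the day after drug initiation, and nothing links them to earlier stays. A reader might also see differential baseline residence in 108 teriparatide against 72 risedronate censorings. The counts do not support that, because median follow-up is longer on teriparatide: 192 against 148 days in Optum and 234 against 148 in MarketScan. Longer time at risk could explain much or all of the difference.

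**Conclusion.** The contradiction holds. Section 6.3.2 states a cohort exclusion, Section 5.2.2 says the flowchart summarizes all criteria, and the flowchart reaches 4,728 and 8,029 exactly without it. The unmatched Table 1 confirms that no later step applied it before matching.

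It follows that women with a nursing home admission before or on the index date may be in the cohort, with baseline drug histories that the plan's own reasoning treats as incomplete. A reader might go further and say that such women are enrolled and misclassified as new users. The documents do not show this: they report no count, and the inference depends on the missing row meaning a missing step.

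The size of any bias is unknown, and so is its direction. The effect on power is likely small: pooled power stays at 92.8% or more for an assumed loss of up to 10%. The issue is the validity of the new-user definition and the baseline drug covariates, not precision. It is worth correcting now because Section 13 is still blank.

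**What to change.** Before the Section 13 comparative analyses:

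1. Apply the exclusion for nursing home admission in the baseline look-back up to and including the index date. Use the same definition as the censoring event, and state the look-back window. The sponsor should choose that window in view of the drug look-backs it protects, which run from 30 to 730 days.
2. Add a flowchart row in Section 5.3 with the count per database, and an Appendix A entry if there is not one already.
3. Re-run matching, Table 1, the matched N and the Section 10 power.

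If the exclusion was already applied inside another row, name that row and show the count there. If it was dropped, reconcile Section 6.3.2 with Section 5.3 and report by arm how many such women the cohort includes.

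The cost is one added criterion, a re-run of the matching and balance steps, and probably a small loss of matched patients. The documents do not show the codes behind the censoring event, so the programming effort cannot be judged from them.
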